9.4 Prior/Concomitant Medications

Prior/concomitant medications will be coded using World Health Organization Drug Dictionary Enhanced (WHO-DDE) B3. The version will be populated in the outputs.

The reported medication will be classified as ‘Prior only’, ‘Prior and concomitant’ or ‘Concomitant only’. These 3 categories are mutually exclusive:

- ‘Prior only’: if the subject has not taken any IP; or if the medication end date (/time) is before IP start date (/time). If the medication end date is partially missing, the medication will only be assigned to ‘Prior only’ if the partial date gives clear evidence that the medication stopped before IP start date (eg, a partial medication stop date of -- Mar 2022 is clearly before an IP start date of 03 Apr 2022).
- ‘Concomitant only’: if the medication start date (/time) is on or after IP start date (/time). If the medication start date is partially missing, the medication will only be assigned to ‘Concomitant only’ if the partial date gives clear evidence that the medication started on or after IP start date.
- ‘Prior and concomitant’: all medications which are not assigned as ‘Prior only’ nor ‘Concomitant only’.

Concomitant medications (ie, medication classified as ‘Prior only’, ‘Concomitant only’ or ‘Prior and concomitant’) will be summarized showing the number and percentage of subjects taking concomitant medications by ATC classification level 4 and preferred term. If the ATC level 4 coding is not available for a preferred term, the next available lower level ATC code will be used. Tables will be provided for the Safety Analysis Set by treatment group and overall.

The following by-subject listing will be provided:

- Prior and concomitant medication.

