8.4 Concomitant Therapies

All drugs and procedures currently being administered to a subject at the time of signing informed consent, and which continue to be taken in addition to investigational product during study participation, are regarded as concomitant therapies.

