8.5.6 Follow-up Telephone Call

On Day 154 (\pm 5 days), the investigator (or delegate) will contact the subject by telephone to collect data on AEs (including acute exacerbation of IPF symptoms) and concomitant medications. The Follow-up Telephone Call should be scheduled to occur 90 days after the last administration of investigational product.

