6.2 Safety Analysis Set

The Safety Analysis Set comprises all subjects who receive any portion of an IV infusion or SC injection of CSL312 or placebo, and analyses will be based on the actual treatment received.

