8.2.2 Durations

Durations (eg, the duration of an AE) are calculated in days as:

- Event end date – event start date + 1, if end time or start time not available;
- Event end date / time – event start date / time, if both end time and start time available.

Thus, there will be no duration of 0 if end time or start time are not available. If an AE has missing or partially missing start or end date, no duration will be calculated.

To transform durations or elapsed times, which are calculated in days into weeks, divide the number of days by 7; to report in months, divide the number of days by 30.4375; to report in years, divide the number of days by 365.25. These algorithms return decimal numbers, and ignore the actual numbers of days in the months or years (the calendar days) between start date and stop date. The "year" used in these algorithms is 365.25 days long, and the "month" is one-twelfth of that year.

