8.4 Study Periods Relative to Treatment

All data will be assigned to 1 of the 3 study time periods defined below.

- **Pre treatment** is defined as the time before the subject's first date / time of IP (Day 1).
- **On-treatment** (Treatment and Observation Period) is defined as the time from first date / time of IP up to Week 14 (Day 1 to Day 92).
- **Post treatment** begins after the end of the Treatment and Observation Period (Day 92) and continues through the Follow-up visit (follow-up telephone call) (Day 154).

9 Study Population

Unless otherwise stated, all tables and listings in this section will be based on the Safety Analysis Set.

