13.2.1 Pulmonary Function Data Analyses

The Safety Analysis Set will be used for this analysis.

The absolute change from baseline in FVC and percent predicted FVC over time will be analyzed using the same MMRM as for FXIIa-mediated kallikrein activity, with treatment group, and visit as fixed effects, and baseline as a covariate. Interactions with visit will be included for treatment group and baseline. Mean difference in LSMeans between treatment groups and its 95% confidence interval will be provided at each time point, assuming that the data is normally distributed. If the data are not normally distributed by visual inspection of residual plots or statistical testing, an appropriate data transformation may be done. There is no imputation of missing FVC data planned.

For FVC and percent predicted FVC the observed values and absolute change from baseline will be summarized by nominal time point by descriptive statistics (n, mean, SD, minimum, Q1, median, Q3, maximum). The descriptive summary for both parameter will be provided for Safety Analysis Set and PD Analysis Set.

Mean (\pm SD) time profiles for observed values and absolute change from baseline for FVC and percent predicted FVC will be plotted by using nominal (planned) time points.

The number and proportion of subjects with $\geq 5\%$ or $\geq 10\%$ absolute (absolute change from baseline) or relative (percent change from baseline) decline in FVC percent predicted at Day 92 will be presented.

The absolute change from baseline in FVC at Day 92 versus the absolute change from baseline in FXIIa-mediated kallikrein activity at Day 92 will be graphically displayed by a scatter plot. The Pearson correlation coefficient and Spearman correlation coefficient by treatment group will displayed. Those scatter plots of absolute change in FVC at Day 92 versus the absolute change at Day 92 will be repeated for all PD parameter (FXII

concentration and aPTT) and biomarkers (CCL-18, PAI-1, SP-A, SP-D, YKL-40, PROC3, PROC6, C3M, C6M).

A second series of those scatter plots will be provided by using the percent change from baseline in FVC at Day 92 versus the percent change from baseline in PD parameter (FXIIa-mediated kallikrein activity, FXII concentration, aPTT) and biomarkers (CCL-18, PAI-1, SP-A, SP-D, YKL-40, PROC3, PROC6, C3M, C6M) at Day 92.

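### The concomitant-medication table in SAP 9.4 includes the 'Prior only' class, so drugs stopped before the first dose are counted as concomitant

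*SAP*

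**What the plan says.** SAP 9.4 uses three classes. 'Prior only' covers a drug whose end date precedes the first dose of investigational product (IP), or any drug of a subject who took no IP. 'Concomitant only' covers a drug started on or after the first dose. 'Prior and concomitant' is everything else. The section calls the classes mutually exclusive, and the remainder class makes them exhaustive.

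The summary rule then reads: "Concomitant medications (ie, medication classified as ‘Prior only’, ‘Concomitant only’ or ‘Prior and concomitant’) will be summarized". It counts subjects by ATC level 4 and preferred term. On population it says: "Tables will be provided for the Safety Analysis Set by treatment group and overall". SAP 6.2 defines that set as "all subjects who receive any portion of an IV infusion or SC injection of CSL312 or placebo". The only other output in SAP 9.4 is a by-subject listing of prior and concomitant medication.

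Protocol 8.4 says that drugs in use at consent "which continue to be taken in addition to investigational product during study participation, are regarded as concomitant therapies". Protocol Table 7 collects previous medications back to 6 months before Screening. Protocol Table 6 bars antifibrotics within 28 days before randomization and through Day 92, except at the investigator's discretion for disease progression, and Table 5 states the same exception.

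**The concern.** A table labelled concomitant ought to show what subjects took alongside the study drug. This one also counts drugs they had already stopped, and such records are to be expected given the six-month look-back and the antifibrotic washout.

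Antifibrotic use bears on how the exploratory FVC and biomarker comparisons are read. A subject who washed out nintedanib before randomization and a subject who started it on study for progression would sit in the same preferred-term row. A reader could not tell how many subjects in each arm had an antifibrotic on board when FVC was measured.

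For anticoagulants the point is weaker. Use other than LMWH through Day 92 is prohibited, so it would also appear as a protocol deviation, listed in every case and summarized by arm if major (SAP 9.2).

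There is a separate, minor version lag. SAP 7.1 treats any COVID-19 vaccination as a deviation and places all vaccinated subjects in the deviation listing. The SAP is based on the protocol through Amendment 2. Amendment 3 removed exclusion criterion 8, and Table 5 now permits SARS-CoV-2 vaccines.

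**Working it through.** **Class logic.** The plan gives no figure to reproduce. For a given drug and arm, let P be the subjects with a 'Prior only' record and O the subjects with a record in either of the other two classes.

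- Row as written: |P ∪ O|
- Row for concomitant use: |O|
- Excess: |P ∪ O| − |O| = |P \ O|, the subjects whose only use ended before IP

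The no-IP branch of 'Prior only' cannot contribute, because the table is restricted to treated subjects. With 40 planned per arm (SAP 4.4) the excess lies between 0 and 40. Without usage counts it cannot be narrowed.

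**Can on-study antifibrotic use be recovered from other outputs?**

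- SAP 9.3 shows previous nintedanib or pirfenidone treatment by arm. Subtraction gives |P ∪ O| − |P| = |O \ P|, which omits anyone with both prior and on-study use. It is a lower bound on |O|, not the count.
- Use permitted for progression is not a deviation, so the deviation summary does not show it.
- The by-subject listing holds the records but is not a by-arm count.

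**Recording windows.** These show what the table spans. They do not estimate bias.

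Inputs:

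- Look-back of 6 months (Protocol Table 7). SAP 8.2.2 gives the conversion, "to report in months, divide the number of days by 30.4375": 6 × 30.4375 = 182.6 days
- Screening 1 to 28 days before Day 1 (Protocol 3.1)
- On-treatment period, Day 1 to Day 92 (SAP 8.4): 92 days
- Follow-up on Day 154, when site staff "will contact the subject by telephone to collect data on AEs (including acute exacerbation of IPF symptoms) and concomitant medications" (Protocol 8.5.6): 154 − 92 = 62 further days

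| Quantity | 1-day screening | 28-day screening |
|---|---|---|
| Before IP | 182.6 + 1 = 183.6 | 182.6 + 28 = 210.6 |
| Total as written | 183.6 + 154 = 337.6 | 210.6 + 154 = 364.6 |
| Share before IP | 183.6 / 337.6 = 54.4% | 210.6 / 364.6 = 57.8% |
| Share on-treatment | 92 / 337.6 = 27.2% | 92 / 364.6 = 25.2% |

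Carrying the ±5-day window on the Day 154 call through widens the total to 332.6–369.6 days, the share before IP to 53.6%–58.6% and the on-treatment share to 24.9%–27.7%.

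Without 'Prior only', the nominal window is Day 1 to Day 154: 92 / 154 = 59.7% on-treatment and 62 / 154 = 40.3% after Day 92. The FVC responder summary is fixed at Day 92 ("decline in FVC percent predicted at Day 92 will be presented"), so even the corrected table includes drug use that began after that measurement.

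**The case against.** The best defence is that a combined display was intended. The section is headed for both kinds of medication, speaks of tables in the plural, and sets partial-date rules that would be pointless if no output used the classes. On that reading the fault is a loose label. But where this SAP means both kinds it says so, as it does for coding and for the listing. The summary rule alone says concomitant, and it counts subjects taking concomitant medications. Even a combined table would carry the wrong label and leave the two kinds of use unseparated by arm.

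The effect is also limited, and this stands. The table is descriptive, FVC is exploratory, SAP 8.3 has no formal plans to investigate covariates, and with about 80 subjects the listing can be searched by hand.

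Protocol 8.4 is not a full definition of concomitant use, since it covers only drugs in use at consent. That is correct. The SAP conflicts with it only for such drugs that stop before dosing; the main inconsistency is within SAP 9.4 itself.

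The window arithmetic adds little, because the table counts subjects rather than days. That is fair.

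On vaccines, SAP version 1.0 (28 April 2022) predates Amendment 3 (18 October 2022). Protocol 13.4 ties deviations to the approved protocol, and SAP 9.2 leaves the final decision to blinded review. What remains is mainly the unconditional listing rule.

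**Conclusion.** The point holds. As worded, SAP 9.4 reports drugs stopped before the first dose as concomitant, and nothing elsewhere in the SAP corrects it; SAP 5 declares only a change to the Screened Analysis Set. Each row is inflated by the subjects with pre-IP use only, between 0 and 40 per planned arm. The actual number depends on usage data the documents do not contain.

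For washed-out antifibrotics, the conclusion assumes an end date that is complete, or partial but clearly before the first dose. Less certain end dates fall into 'Prior and concomitant' under the SAP's own rule and would stay in the table after correction.

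This should be corrected before database lock: it is a stated rule that gives wrong by-arm counts. The vaccine point affects only a flag in a listing.

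**What to change.** In SAP 9.4, define the concomitant table as 'Concomitant only' plus 'Prior and concomitant', and present 'Prior only' in its own table. The preferred-term rows will then show nintedanib and pirfenidone use by arm, though through Day 154. If a by-arm antifibrotic row is added to help interpret FVC and biomarkers, limit it to use from the first dose through Day 92, the on-treatment period in SAP 8.4.

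In SAP 7.1, flag a COVID-19 vaccination as a deviation only where the protocol version in force for that subject at the time prohibited it. Keep the vaccine listing and the listing of events within 7 days of vaccination.

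The cost is one phrase deleted, one table added (plus the optional row) and one paragraph updated. No new data are needed. Protocol 10.3.1 and SAP 3 leave room for these changes until database lock.

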9.5 Study Population - Derived Variables

Derivation of Body Mass Index (BMI)

BMI data will be used from eCRF as collected. In case of missing BMI, BMI will be calculated using the following formula:

$$\text{BMI (kg/m}^2\text{)} = \text{Weight (kg)} / [\text{Height (m)}]^2,$$

using the height measured at Screening and the weight measured at Day 1 (if available). If weight at Day 1 is not available, the assessment at Screening will be used (if available). If neither is available, then BMI is missing.

10 Efficacy Analyses

There are no primary or secondary efficacy endpoints in this study. The analysis of FVC as exploratory efficacy endpoint is described in [Section 13.2.1](#).

10.1 Treatment Compliance

The calculation of overall compliance is based on receiving the IV loading dose and all 3 SC injections of IP. An infusion or injection of at least 80% of the planned volume will satisfy the criteria of receiving a compliant infusion or injection at each of the 4 visits. The following summaries will be provided by treatment group for the Safety Analysis Set:

- The number of subjects receiving all 4 doses of IP;
- The number of subjects receiving at least 80% of the planned infusion/injection volume at each visit.

A by-subject listing will be provided including:

- By infusion/injection: the randomized and actual treatment administered, planned and actual volume of IP, individual and categorized compliance;
- Overall (across all IP doses): cumulative planned and cumulative actual volume of IP, individual and categorized compliance, number of doses of IP.

Calculation of compliance and extent of exposure (as described in Section 11.1) will be based on drug accountability data collected by eCRF.

11 Safety Analyses

The safety analyses will be based on the Safety Analysis Set as defined in [Section 6](#) and on the treatment which the subject received.

11.1 Extent of Exposure

Exposure to the IP will be descriptively summarized by treatment group:

- Number of subjects receiving loading dose;
- Summary statistics for loading dose received;
- Summary statistics for Total dose received (mg) per visit and overall;
- Summary statistics for Total volume received (ml) per visit and overall.

The listing of individual subject data will include all variables presented in the summary tables.

11.2 Adverse Events

AEs will be coded using the MedDRA dictionary (the MedDRA version will be populated in the tables output). AEs will start to be collected upon the subject's signing of the informed consent form (ICF). TEAEs, defined as AEs starting on or after the date (and time if available) of the first administration of IP (IV loading dose) through the end of the Treatment and Observation Period, will be summarized. The summary will be given by treatment group and overall. All AEs regardless of whether they were treatment-emergent or not will be listed.

Where AE start dates and/or times are missing or partially missing, AEs will be assumed to be treatment-emergent, except if the partial start dates and/or times or the AE end date and/or time indicate that the AE started before the first administration of IP (Table 2).

Table 2 TEAE Assignment in Case of Missing AE Start Date Elements

Missing elements of AE start	Rule	
Regardless of any missing information for AE start: AE end date / time < IP start date / time		non TEAE
Otherwise (ie, if AE end date / time \geq IP start date / time)		
- all		TEAE
- day and month	AE start year \geq IP start year	TEAE
	AE start year < IP start year	non TEAE
- day	AE start month / year \geq IP start month / year	TEAE
	AE start month / year < IP start month / year	non TEAE
- time	AE start date \geq IP start date	TEAE
	AE start date < IP start date	non TEAE

If AE start dates or end dates are missing or partially missing for an AE, no duration will be calculated. A missing category will be shown in summary tables by severity in case the severity is missing (the same is applicable for relationship to study treatment). No imputations for missing AE information will be done.

The AESIs defined for this study are:

- Bleeding events - Standardised MedDRA Query "Haemorrhages (SMQ)" (narrow)
- Thromboembolic events (TEE) - Standardized MedDRA Query "Embolic and thrombotic events (SMQ)" (narrow) consisting of:

- Embolic and thrombotic events, arterial (SMQ);
 - Embolic and thrombotic events, venous (SMQ);
 - Embolic and thrombotic events, vessel type unspecified and mixed arterial and venous (SMQ).
- Severe Hypersensitivity including anaphylaxis - Standardised MedDRA Query “Hypersensitivity (SMQ)” (broad), “Anaphylactic reaction (SMQ)” (broad), and “Anaphylactic/anaphylactoid shock conditions (SMQ)” (broad). Here, broad scope includes narrow and broad search.

An overview summary of TEAEs, including number and percentages of subjects as well as the number of events will be provided including the following:

- Any TEAE;
- TEAEs related to study treatment;
- TEAEs in each severity category;
- TEAEs leading to discontinuation of study treatment (obtained from AE eCRF);
- TEAEs leading to study withdrawal (obtained from “End of Treatment” or “Conclusion of Subject Participation” eCRF);
- TEAEs leading to dose adjustments or dose interruptions;
- Treatment-emergent AESIs;
- Treatment-emergent AESIs related to study treatment;
- Serious TEAEs;
- Serious TEAEs related to study treatment;
- Fatal TEAEs.

COVID-19 associated TEAEs will be included in AE overview table as (as described in [Section 7.1](#)):

- Any TEAE (related/not related);
- Serious TEAE (related/not related);
- Fatal TEAE (related/not related);

- TEAE leading to discontinuation of study treatment (obtained from AE eCRF) (related/not related);
- TEAE leading to dose adjustments or dose interruptions (related/not related);
- TEAE leading to study withdrawal (related/not related);
- TEAE by maximum severity (mild, moderate, severe, missing).

The following frequency tables will be generated for TEAEs, including number and percentages of subjects and the number of events:

- TEAEs by SOC and preferred term;
- TEAEs by preferred term;
- TEAEs by SOC, preferred term, and maximum severity (without number of events);
- Related TEAEs by SOC and preferred term;
- Related TEAEs by preferred term;
- Treatment-emergent AESIs by preferred term;
- Serious TEAEs by SOC and preferred term;
- Related serious TEAEs by SOC and preferred term;
- TEAEs with result in drug discontinuation;
- TEAEs related to COVID-19 infection.

AEs will be presented in summaries by decreasing overall frequency (overall frequency as the number of subjects with that AE beginning with the SOC, followed by preferred term). If 2 AEs have the same overall frequency, the AEs will be ordered alphabetically.

The following by-subject listings will be provided:

- All AEs;
- SAEs;
- AEs leading to study withdrawal or permanent discontinuation of study treatment;
- AESIs by type of AESI;
- Subjects receiving COVID-19 vaccine;
- AEs occurring within 7 days after COVID-19 vaccine administration.

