2.1.2 Primary Endpoints

Endpoints	Summary Measure
Subjects experiencing treatment-emergent adverse events (TEAEs) including: 
 • SAEs • AESIs • CSL312-induced ADAs • Clinically significant abnormalities in laboratory assessments that are reported as AEs 	Number and proportion of subjects experiencing the specified safety events after treatment with investigational product (CSL312 or placebo)

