3.4 Planned Study Duration

The duration of the study for an individual subject is expected to be up to 6 months. This estimate is based on:

- Screening / Washout Period of up to 28 days
- 14-week Treatment and Observation Period
- Follow-up Telephone Call at 90 days after the last investigational product administration

The overall study duration (ie, first subject's Screening Visit to last subject's Follow-up Telephone call) will be approximately 17 to 19 months.

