9.1 Definitions

9.1.1 Adverse Event

As per the ICH Topic E2A (Clinical Safety Data Management: Definitions and Standards for Expedited Reporting), an AE is any untoward medical occurrence in a patient or clinical investigation subject administered a pharmaceutical product and which does not necessarily have a causal relationship with this treatment. An AE can, therefore, be any unfavorable and unintended sign (including an abnormal, clinically significant laboratory finding), symptom, or disease temporally associated with the use of a medicinal (investigational) product, whether or not it is considered related to the medicinal (investigational) product.

The period of observation for AEs extends from the time the subject gives informed consent until the end of study (see [Section 9.4](#) for further details).

AEs may include:

- Exacerbation (ie, an increase in the frequency or severity) of a pre-existing condition. Illness present before study entry should be recorded in the medical history section of the eCRF and only be reported as an AE if there is an increase in the frequency or severity of the condition during the study.
- A clinical event occurring after consent but before investigational product administration.
- Intercurrent illnesses with an onset after administration of investigational product.

AEs do not include:

- Events identified at Screening that meet exclusion criteria
- Medical or surgical procedures (the condition that leads to the procedure is the AE)
- Situations where an untoward medical occurrence has not taken place. For example:
 - Planned hospitalizations due to pre-existing conditions that have not worsened.
 - Hospitalizations that occur for procedures not due to an AE (eg, cosmetic surgery).
 - Hospitalizations for a diagnostic procedure where the hospital stay is less than 24 hours in duration or for normal management procedures (eg, chemotherapy).
 - Overdose of investigational product or any concomitant therapy that does not result in any adverse signs or symptoms.

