10.3.3 Safety Analyses

TEAEs will be coded using the Medical Dictionary for Regulatory Activities (MedDRA) version 24.1 (or higher). A TEAE is defined as an AE reported at or after the start of the first administration of study treatment. Only TEAEs will be summarized.

An overview summary of TEAEs, including counts and percentages of subjects with any of the following events, will be produced:

- TEAEs
- TEAEs related to study treatment
- TEAEs leading to permanent discontinuation of study treatment
- Serious TEAEs
- Serious TEAEs related to study treatment
- Fatal TEAEs

- Fatal TEAEs related to study treatment
- TEAEs by severity
- Treatment-emergent AESIs

TEAEs will be summarized by system organ class and preferred term. TEAEs will also be summarized by causality and severity. All TEAE summaries will be provided for each treatment group and overall.

The number and percentage of subjects with plasma anti-CSL312 antibodies will be summarized by treatment group and overall.

Laboratory evaluations (hematology, biochemistry, and urinalysis) will be summarized descriptively by treatment group.

Change from Baseline in DL_{CO} will be summarized using descriptive statistics by treatment group.

The Safety Analysis Set will be used for the safety analyses unless indicated otherwise.

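### The SAP defines a TEAE by start date alone, so an adverse event that begins before first dose and worsens afterwards can be left out of the primary safety tables

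*SAP*

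**What the plan says.** **Collection.** AE collection starts at consent (Protocol 9.4, SAP 11.2). Protocol 3.4 allows a "Screening / Washout Period of up to 28 days" before dosing. Protocol 9.1.1 counts as an AE "A clinical event occurring after consent but before investigational product administration".

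**Classification.** SAP 11.2 reads "TEAEs, defined as AEs starting on or after the date (and time if available) of the first administration of IP (IV loading dose", with the window closing at the end of the Treatment and Observation Period. It says nothing about a later change in severity or seriousness. SAP Table 2 deals only with incomplete start dates. Protocol 10.3.3 reads "A TEAE is defined as an AE reported at or after the start of the first administration of study treatment". Apart from the Screened Analysis Set, SAP Section 5 reports no change from the protocol.

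**Reporting.** The primary summary measure is "Number and proportion of subjects experiencing the specified safety events after treatment with investigational product (CSL312 or placebo" (Protocol 2.1.2). For the AE tables, Protocol 10.3.3 states "Only TEAEs will be summarized". Events that are not treatment-emergent go to listings: "All AEs regardless of whether they were treatment-emergent or not will be listed" (SAP 11.2).

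**Worsening.** Protocol 9.1.1 also lists as an AE "Exacerbation (ie, an increase in the frequency or severity) of a pre-existing condition". Its recording instruction is written for illness that was there before study entry, which goes into medical history.

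**The concern.** The primary measure asks what happens to subjects after treatment. An event that begins in Screening and becomes serious or fatal on treatment is such an outcome. A rule that looks only at onset treats it as a pre-treatment event.

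Worsening of something already present is an ordinary way for a safety signal to appear in a progressive lung disease. The pre-dose period is also a washout, in which antifibrotics and other prohibited drugs are withheld, so new respiratory complaints there are plausible. What is at stake is whether the by-arm AE tables show such worsening, above all the serious and fatal rows, where counts are likely to be small.

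**Working it through.** **1. Denominator.** Sample size sections (Protocol 10.1, SAP 4.4): 35 evaluable per arm, 12% dropout. 35 / (1 − 0.12) = 39.8, rounded up to 40 per arm and 80 in total. Reverse check: 80 × 0.88 = 70.4. The plan's 80 and 70 are reproduced. The point uses only the 40.

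**2. The rules applied to example records** (first dose on Day 1):

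| Record | Protocol 10.3.3 | SAP 11.2 | SAP 11.2 with a worsening clause |
|---|---|---|---|
| A. One record, onset Day −10, reported before dosing, worse or serious on Day 20 | not TEAE | not TEAE | TEAE |
| B. Same case, worsening entered as a new record starting Day 20 | TEAE | TEAE | TEAE |
| C. Onset Day −2, first reported Day 8, no worsening | TEAE | not TEAE | not TEAE |
| D. Start day missing, same month as first dose, not ended before dosing | depends on report date | TEAE (Table 2) | TEAE |

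A is the gap. B shows that the result turns on how the site records the worsening. C shows that protocol and SAP give different answers for the same event.

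**3. Where record A goes.** The AE overview and frequency tables in SAP 11.2 are built on TEAEs, including the serious, fatal and AESI rows, so A is in none of them. It appears in the listings of all AEs and, where it qualifies, of SAEs and AESIs.

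**4. Is B required?** Protocol 9.1.1 makes exacerbation of a pre-existing condition an AE. For laboratory values already abnormal at Screening, it lifts the reporting exemption if a further change amounts to an exacerbation. Neither provision states what to do with an AE that began between consent and dosing. Protocol 9.6.1 asks the investigator to follow an AE's course until it resolves or stabilizes, and 9.6.3 asks for SAE follow-up information in the eCRF. Both are compatible with updating the existing record. Neither document instructs the site to open a new one.

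**5. Size.** The documents give no rate for record A. Taking k such subjects in one arm as an assumption, the largest shift in a row is k/40:

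- k = 1: 1/40 = 2.5 percentage points
- k = 2: 2/40 = 5.0
- k = 3: 3/40 = 7.5

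A subject who already counts in a row through another event does not move it.

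**The case against.** The strongest reply is that Protocol 9.1.1 already treats an exacerbation as an AE in its own right. Entered that way, it has a post-dose start and is counted. Study entry is not defined as consent, so the provision may be meant to reach Screening-onset events, and record handling may be settled in eCRF guidance that is not available here. This stands as far as it goes: a reader might infer that such worsening is never counted, and the documents do not support that. They leave the matter open.

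Three further limits also stand.

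- A reader might take Table 2 as fixing these events as non-TEAE. It covers only incomplete start dates, and its default favors TEAE.
- A reader might infer that the worsening is invisible in every by-arm output. Laboratory values (with shift tables), vital signs, ECG, DLCO and FVC are summarized by arm, and anti-drug antibodies are counted from test results. The IDMC outputs in SAP 4.5.1 are named as SAEs, AEs and AESIs, with supporting listings.
- Some examples are weak. Active bleeding is an exclusion criterion. Cough or dyspnea from IPF will often predate study entry, which is the case Protocol 9.1.1 addresses expressly.

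None of this supplies the missing clause, settles the recording rule or reconciles the two TEAE definitions.

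**Conclusion.** The point holds as a gap in the definition behind the primary safety tables and should be corrected. A pre-dose AE with a known start, kept as one record, is left out of the TEAE tables even if it becomes serious or fatal after dosing. Whether that happens depends on a recording practice that neither document fixes. The undeclared difference between protocol and SAP is certain from the text.

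The effect is at most 2.5 percentage points per omitted subject in an arm of 40, assuming all 40 are treated. A reader might infer a distortion of 5 to 10 points by assuming that 10% to 20% of 80 subjects have a Screening-onset AE and that a quarter of these worsen (80 × 0.10 × 0.25 = 2; 80 × 0.20 × 0.25 = 4; 2/40 = 5%, 4/40 = 10%). Those rates are not in the documents, and the result puts every case in the CSL312 arm. The same rates within one arm give 1 to 2 subjects, or 2.5 to 5 points. The rule is the same in both arms, and SAP 4.1.1 states that there is no primary hypothesis, so the consequence is incomplete description rather than a faulty test.

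**What to change.** Define a TEAE in SAP 11.2 as an AE that starts on or after first IP, or that starts before first IP and increases in severity or becomes serious on or after first IP. Put the same definition in Protocol 10.3.3 in place of the rule based on reporting, and declare the change in SAP Section 5.

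Implement it by one route only:

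- reclassify the existing record from the date of worsening; or
- have sites enter the worsening as a new AE record with its own start date, leaving the pre-dose record non-TEAE.

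Using both would count one worsening as two events in tables that report event numbers.

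The cost is wording in two documents, an eCRF instruction or field for the date of worsening, and slightly higher TEAE counts in both arms. Whether the current eCRF captures that date cannot be seen from the documents. The sample size does not change.

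A separate matter will come up in the alignment: SAP 11.2 ends the TEAE window at Day 92, while Protocol 10.3.3 sets no end and AE collection runs to the Day 154 call, 154 − 92 = 62 days later.
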